For the majority of patients with relapsed or refractory (R/R) AML with unfavorable prognostic features, intensive chemotherapy or other standard treatment options have poor outcomes with complete remission rate (CRR) no higher than 15% and median overall survival (mOS) less than 6 months (Estey, 1996; Ritchie, 2013; Roboz, 2014; Perl, 2019). Among AML patients who relapsed after having achieved a first complete remission (CR1), about 45% do so within 6 months, 75% within 12 months and 85% within 18 months (Breems, 2005; Estey 1996). While the minority of patients who experience relapse after more than 1 or 2 years in CR1 generally fare better, chances to achieve long term disease control for the majority of patients with R/R AML are dismal, exemplified by 3-year survival of 11% for adults up to 55 years old and 6% for patients above age

55 determined by analysis of eight pooled Eastern Cooperative Oncology Group (ECOG) studies for relapsed AML (Rowe, 2010). More recently, Onureg, an oral formulation of the hypomethylating agent azacitidine, in AML maintenance demonstrated improvement in both progression free survival (PFS) and overall survival (OS) for patients in CR1 that are ineligible for allogeneic stem cell transplantation (SCT) (Wei, 2020). While this is encouraging, the experience needs to be built upon (Reville, 2021). Although the approved combination regimen of venetoclax and azacitidine (DiNardo, 2020) has improved response rates and survival in this patient population compared with prior regimens (see Section 1.2.3), complete remission (CR) rates remain low and rates of eventual relapse are high, and this remains a population with a high unmet need. Continuing research efforts are needed to develop new agents and treatment regimens that are tolerable and effective in R/R AML patient population, and the addition of investigational agents to the combination of venetoclax and azacitidine may increase the remission rate and prolong survival, therefore addressing an important unmet medical need in patients with newly diagnosed (ND) and R/R AML.

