Data on R/R AML are scarce and heterogenous. Outcomes in patients with R/R AML are dismal, with a median OS of 3 to 7 months, and there is no approved standard of care (SOC). A systematic literature review and meta-analysis assessed overall response rate (ORR), and rates of CR/CRi for R/R AML subjects treated with venetoclax or venetoclax plus HMA/low-dose cytarabine (LDAC)

Protocol CA059-001 Amendment 3.0

(Bewersdorf, 2020b). This systematic review and meta-analysis of venetoclax treatment in R/R AML included 7 studies with a total of 224 subjects and demonstrated an ORR of 38.7% and a CR rate of 19% for R/R AML subjects treated with venetoclax plus HMA/LDAC. Moreover, the meta-analysis showed that prior treatment with HMA did not preclude a response to subsequent venetoclax-based treatment.

The safety of venetoclax in combination with azacitidine (N = 283) versus placebo in combination with azacitidine (N = 144) was evaluated in the VIALE-A study. Subjects were randomized to receive venetoclax 400 mg orally once daily (QD) after completion of the ramp-up phase in combination with azacitidine (75 mg/m² either IV or SC on Days 1 through 7 of each 28-day cycle) or placebo in combination with azacitidine. Serious adverse reactions were reported in 83% of subjects who received venetoclax in combination with azacitidine, with the most frequent ( $\geq$  5%) being febrile neutropenia (30%), pneumonia (22%), sepsis (excluding fungal; 19%), and hemorrhage (6%). Fatal adverse reactions occurred in 23% of subjects who received venetoclax in combination with azacitidine, with the most frequent ( $\geq$  2%) being pneumonia (4%), sepsis (excluding fungal; 3%), and hemorrhage (2%).

In subjects with AML who followed the current 3-day ramp-up dosing schedule and the tumor lysis syndrome (TLS) prophylaxis and monitoring measures, the rate of TLS was 1.1% in subjects who received venetoclax in combination with azacitidine (VIALE-A). In subjects with AML, baseline neutrophil counts worsened in 95% to 100% of subjects treated with venetoclax in combination with azacitidine, decitabine, or low-dose cytarabine. Neutropenia can recur with subsequent cycles.

A detailed description of the chemistry, pharmacology, efficacy, and safety of venetoclax in combination with azacitidine is provided in the Summary of Product Characteristics (SmPC) and/or package insert approved in the local country (venetoclax Package Insert, 2020) (venetoclax SmPC, 2022).

[figure not shown]

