## 6.3.2 Efficacy Long Term Follow up

After EOT visit, subjects without documented progression of disease (or relapse) or start of a new anticancer therapy will have efficacy evaluations

or until progression of disease (or relapse), initiation of a new anticancer therapy, withdrawal from the study, death, or the End of Trial, whichever comes first. A bone marrow evaluation will be completed

and as clinically indicated during the Follow-up Period.

Information (including dates) on new anticancer therapies initiated will be collected until withdrawal from the study, death, or the End of Trial, whichever comes first.

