# 9.6 Efficacy Analysis

The key efficacy variables are CRR (defined as CR + CRi + CRh for AML; CR for MDS) and ORR (all responses of CR [ie, CRMRD-, morphologic CR, CRh, CRi] + MLFS + PR for AML and CR + CRh + marrow CR + PR for MDS) by disease -appropriate response criteria. For dose expansion, efficacy variables to be analyzed include CRR and ORR, duration of remission, duration of response, stable disease rate (MDS only), relapse-free survival, event-free survival, progression-free survival, time to remission/response, transfusion independence, time to AML transformation for MDS subjects, and OS rates at 6 and 12 months. Point estimates and 2-sided 90% exact Clopper-Pearson confidence intervals of CRR and ORR will be reported. For time to event endpoints, Kaplan-Meier survival analyses will be performed. The PFS and overall survival rate will be measured and reported at pre-specified time points (ie, 6 months, 12 months).

Exploration of PK, PD, safety and activity relationships may be assessed.

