# 9.7 Safety Analysis

The primary objective of this study is to define the RP2D of CC-95251 alone and in combination with azacitidine in eligible subjects with AML or MDS and in combination with azacitidine and venetoclax in eligible subjects with AML.

The

final determination of RP2D will be decided by the SRC.

Statistical analyses will be performed by dose level or dose schedule and a combination product as needed or applicable. Study data will be summarized for disposition, demographic and baseline characteristics, exposure, efficacy, safety, PK, and PD per respective analysis population defined in Section 9 as applicable. All analyses will be descriptive in nature.

Adverse events, including treatment-emergent adverse events, will be graded by NCI CTCAE version 5 grades, except for CRS and TLS, which will be graded according to the revised CRS grading system ([Lee, 2014] and Cairo-Bishop TLS grading system [Cairo, 2004], respectively). The frequency of AEs will be tabulated by Medical Dictionary for Regulatory Activities (MedDRA) system organ class and preferred term. Grade 3 or higher AEs, AEs leading to discontinuation of study treatment or to death, study intervention-related AEs, and SAEs will be tabulated separately. Changes from baseline in selected laboratory analytes for example transfusion dependence (platelet count or red blood cell [RBC] transfusion units), vital signs, and will be summarized.

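### The blanket Kaplan-Meier rule takes in time to remission/response with no visible handling of non-responders; censoring them at death, progression or new therapy would overstate the probability of response

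*Combined protocol and SAP*

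**What the plan says.** Section 9.6 lists the efficacy variables for dose expansion, among them "progression-free survival, time to remission/response, transfusion independence, time to AML transformation for MDS subjects, and OS rates at 6 and 12 months". Response itself is reported as a proportion: "Point estimates and 2-sided 90% exact Clopper-Pearson confidence intervals of CRR and ORR will be reported". One method then covers the timing variables: "For time to event endpoints, Kaplan-Meier survival analyses will be performed". No endpoint is excepted, and Statistical Methods in the Protocol Summary repeats the rule. The only time points that 9.6 fixes for reporting are 6 and 12 months, for PFS and OS.

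On follow-up, Section 6.3.2 continues post-treatment efficacy evaluation "or until progression of disease (or relapse), initiation of a new anticancer therapy, withdrawal from the study, death, or the End of Trial". Section 6.4 likewise ends scheduled disease assessments at progression or new therapy and allows later contact by telephone.

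The readable text does not define time to remission/response. It does not say whether all subjects or only responders are analysed, gives no censoring rule for non-responders, and names no cumulative-incidence method. Some of this may be out of sight: the population descriptions in Table 13 are blacked out, and the text after Table 3, which marks the efficacy endpoint with a footnote, is garbled. Table 3 classes the endpoint as secondary, and Section 9.7 says of the study's analyses: "All analyses will be descriptive in nature".

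**The concern.** Kaplan-Meier treats a censored subject as having the same future chance of the event as those still at risk. For time to response that fails for many non-responders. A subject who dies cannot respond. A subject who progresses or starts another therapy is no longer assessed for response under the plan. If these subjects are censored at that point, their share of future response is credited to them as if they were still under observation, and the curve rises above the proportion who actually respond.

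In relapsed/refractory AML non-responders are the majority, so the effect can be large. The cohorts are single-arm, so the descriptive summaries are the whole efficacy readout. A response curve that levels off above the CRR or ORR would give the same cohort two different response probabilities, with the larger one favouring the drug.

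**Working it through.** **Inputs.** The plan states no figure for time to response, so there is nothing to reproduce. Cohort sizes are blacked out.

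- R/R AML, standard options (Section 1.1.1): "complete remission rate (CRR) no higher than 15% and median overall survival (mOS) less than 6 months". Used as response proportion R = 15% and median m = 6 months.
- R/R AML with venetoclax combinations (Section 1.2.3): "demonstrated an ORR of 38.7% and a CR rate of 19% for R/R AML subjects treated with venetoclax plus HMA/LDAC". The same section gives a median OS of 3 to 7 months in R/R AML. Used as R = 38.7% with m = 3 and 7.
- Treatment-naïve AML on venetoclax plus azacitidine (Section 1.2.3): CR or CRi 66.4%, median OS 14.7 months. This stands in for CRR, which in this protocol also counts CRh.
- Assumed: constant hazards; median OS as the median time to the competing event. Adding progression and new therapy to death would shorten that median, so m = 3 (for 15%) and m = 4 (for 38.7%) are added as assumed values.

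**The mechanism by hand.** Take 20 invented subjects, of whom 3 respond, at months 2, 2 and 4. Three non-responders leave before month 2 and four more between months 2 and 4. At risk: 17 at month 2, and 17 − 2 − 4 = 11 at month 4. Then 1-KM = 1 − (15/17)(10/11) = 19.8%, although 3/20 = 15% responded. If the same non-responders are censored at month 12 instead, 1-KM = 1 − (18/20)(17/18) = 15%.

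**Calibration A: response proportion R reached by time t.** Competing hazard lc = ln 2/m. Response hazard lr solves lr/(lr + lc) × [1 − exp(−(lr + lc)t)] = R. Then 1-KM = 1 − exp(−lr·t). For R = 15%, m = 6, t = 6: lc = 0.1155, lr = 0.0383, and 1-KM = 1 − exp(−0.230) = 20.5%, an excess of 5.5 points.

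| R, m (months) | 1-KM, t = 6 | Excess, t = 6 | Excess, t = 3 | Excess, t = 2 |
|---|---|---|---|---|
| 15%, 6 | 20.5% | 5.5 | 2.7 | 1.7 |
| 15%, 3 (assumed) | 26.8% | 11.8 | 5.5 | 3.6 |
| 38.7%, 3 | 64.1% | 25.4 | 12.8 | 8.5 |
| 38.7%, 4 (assumed) | 58.0% | 19.3 | 9.6 | 6.3 |
| 38.7%, 7 | 49.7% | 11.0 | 5.4 | 3.6 |
| 66.4%, 14.7 | 73.9% | 7.5 | 3.8 | 2.6 |

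**Calibration B: R is the eventual proportion.** Here lr = lc·R/(1 − R), and the cumulative incidence is R × [1 − exp(−(lr + lc)t)].

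| R, m (months) | 6 months: 1-KM vs cumulative incidence | 12 months: 1-KM vs cumulative incidence |
|---|---|---|
| 15%, 6 | 11.5% vs 8.4% | 21.7% vs 12.1% |
| 38.7%, 3 | 58.3% vs 34.7% | 82.6% vs 38.3% |
| 38.7%, 7 | 31.3% vs 24.0% | 52.8% vs 33.1% |
| 66.4%, 14.7 | 42.8% vs 37.8% | 67.3% vs 54.1% |

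At 6 months the differences run from 11.5 − 8.4 = 3.1 points to 58.3 − 34.7 = 23.6 points.

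**Dependence on the censoring rule.** A simulation of calibration B (2000 runs, 20 subjects assumed, 12 months) gave, in the order of the table above:

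- censored at the competing event, mean 1-KM: 21.9%, 75.9%, 52.7%, 67.3%;
- crude proportion responding: 12.0%, 38.5%, 32.9%, 54.0%;
- non-responders censored at end of follow-up: 1-KM identical to the crude proportion;
- responders only: 1-KM reaches 100% by construction, so it describes timing and does not estimate a probability of response.

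**The case against.** The strongest objection is that the bias needs a censoring rule the readable text does not contain. Two ordinary choices, censoring non-responders at end of follow-up or summarising responders only, avoid it, and the missing definition may lie in redacted or lost text. This stands, and it is why the point is conditional. It does not remove the point: the only method visible is Kaplan-Meier without exception, and censoring at the last disease assessment would place the censoring at or near death, progression or new therapy.

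The size is also driven by assumptions. The documents give no timing of response. For an assumed 20 to 40 subjects, half a standard error, 0.5 × √(R(1 − R)/n), is 4.0 to 2.8 points at 15% and 5.3 to 3.7 points at 66.4%. With early responses and death as the only competing event, the excess in those two scenarios is mostly below that. The 38.7% scenarios over 3 months stay above the corresponding 5.4 to 3.9 points, only just so at the 7-month median.

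Some stronger readings are tempting but not supported:

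- A reader might infer that Section 9.6 contradicts itself. It does not: it estimates the probability of response by CRR and ORR, and nowhere says that 1-KM will be reported as one. The conflict is a possible mismatch between outputs.
- A reader might infer that progression or new therapy makes response impossible. Only death does; after the other two, response is no longer assessed.
- A reader might infer that the Kaplan-Meier median would always come too early. With R = 15%, every 6-month value of 1-KM above is below 50%, so no median is reached by then.

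**Conclusion.** The point holds conditionally. On a plain reading, Kaplan-Meier applies to time to remission/response, and nothing readable says how non-responders are handled. If they are censored at death, progression or new therapy, 1-KM exceeds the probability of response in every scenario examined, by about 3 to 25 points at 6 months depending on calibration and competing-event median. The excess falls to about 2 to 4 points for CRR 15% and treatment-naïve AML with death as the only competing event and responses within 2 to 3 months. It is 5 to 13 points for ORR 38.7% with responses within 3 months. These figures rest on constant hazards and on OS as a proxy for the competing-event time.

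A reader might infer that the RP2D or an efficacy conclusion is at risk. The documents do not support that: CRR and ORR are the efficacy variables of focus and are unaffected, and no stated decision rule in the readable text depends on a response curve. This is a cheap improvement to a secondary, descriptive analysis.

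**What to change.** In Section 9.6 and in Statistical Methods of the Protocol Summary, take time to remission/response out of the Kaplan-Meier sentence and add wording such as: *Time to remission/response will be summarised by the cumulative incidence of remission/response in all treated subjects (Aalen-Johansen estimator), with death, progression and new anticancer therapy before response as competing events. Median and range of time to response among responders will be given as a description.*

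With no other censoring, the curve then ends at the observed response proportion and agrees with CRR or ORR. If those rates use a different analysis set (the definitions in Table 13 are not readable), the curve should use the same set.

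The cost is a short text change in two places and a standard estimator. The dates of death, progression and new therapy are already collected. The downside for the sponsor is a less favourable response curve than 1-KM with censoring at those events would show.

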# 9.7 Safety Analysis

The primary objective of this study is to define the RP2D of CC-95251 alone and in combination with azacitidine in eligible subjects with AML or MDS and in combination with azacitidine and venetoclax in eligible subjects with AML.

The

final determination of RP2D will be decided by the SRC.

Statistical analyses will be performed by dose level or dose schedule and a combination product as needed or applicable. Study data will be summarized for disposition, demographic and baseline characteristics, exposure, efficacy, safety, PK, and PD per respective analysis population defined in Section 9 as applicable. All analyses will be descriptive in nature.

Adverse events, including treatment-emergent adverse events, will be graded by NCI CTCAE version 5 grades, except for CRS and TLS, which will be graded according to the revised CRS grading system ([Lee, 2014] and Cairo-Bishop TLS grading system [Cairo, 2004], respectively). The frequency of AEs will be tabulated by Medical Dictionary for Regulatory Activities (MedDRA) system organ class and preferred term. Grade 3 or higher AEs, AEs leading to discontinuation of study treatment or to death, study intervention-related AEs, and SAEs will be tabulated separately. Changes from baseline in selected laboratory analytes for example transfusion dependence (platelet count or red blood cell [RBC] transfusion units), vital signs, and will be summarized.

0.0 Other Tenice

### 9.9 Other Topics

## 9.9.1 Statistical Method for Dose Escalation

Dose-escalation/de-escalation decisions

[figure not shown]
In the columns indicate numbers of evaluable subjects treated at each dose level, and

Dose escalation may be halted once a dose level with acceptable safety and satisfactory antitumor activity has been selected for evaluation in the dose expansion part.

Dose escalation (Part A) may be stopped for the following reasons:

The final determination of RP2D will be decided by the SRC. Each dose level may enroll with the potential to expand to approximately in order to further inform selection of dose and schedule for dose expansion. Enrollment to the highest open dose level will be prioritized if multiple dose levels are open for enrollment.

Regular systematic review of SAEs will serve as the basis for pausing enrollment or prematurely stopping the study. Review of these SAEs, and any decision to pause enrollment or terminate the study, will be determined by the SRC. Decisions to pause enrollment or terminate the study will be communicated promptly to Investigators, to the IRBs and to the appropriate regulatory authorities.

#### 9.9.3 Assessment of Pharmacokinetics

Plasma PK parameters such as  $C_{max}$ ,  $C_{min}$ , AUC,  $t_{max}$ , and CLT of CC-95251 where feasible will be calculated by the noncompartmental analysis (NCA) method from the plasma concentration-time profiles of CC-95251. Other PK parameters may be calculated as appropriate. In addition to the NCA analysis, compartmental analysis may be conducted to estimate PK parameters based on all cycle data for each subject and/or the cohorts.

Summary statistics including number of subjects (N), mean, SD, coefficient of variation (CV%), geometric mean, geometric CV%, median, minimum, and maximum will be provided for CC-95251 concentration by nominal time point, study day, and dose cohort. Mean and individual plots of plasma concentrations will be presented in both original and semi-logarithmic scales. Summary statistics will also be provided for CC-95251 PK parameters by study day and dose cohort and be presented in tabular form.

## 9.9.4 Assessment of Immunogenicity

The incidence of ADAs will be summarized for the Safety Population. In addition, subjects who are positive for ADAs will also be listed. Potential relationships between ADA and safety and efficacy will be assessed.

## 9.9.5 Assessment of Pharmacodynamics and Exploratory Biomarkers

Descriptive statistics (N, mean, SD, median, min, and max) will be provided for baseline, post-baseline values, and changes from baseline or percent change from baseline for biomarkers including receptor occupancy and cytokines by dose cohort (Part A) and visit. Subjects' biomarker results over time will be plotted. Comparison of biomarker levels before and during treatment will be performed by Wilcoxon signed rank test. If sufficient and valid results from biomarker assays can be obtained, the relationship between percent changes in biomarker levels and clinical endpoints including ORR may be explored.

#### 9.9.6 Assessment of Other Exploratory Endpoints

Proportion of subjects achieving MRD negativity at any time on/after treatment with CC-95251 alone, in combination with azacitidine and in combination with azacitidine and venetoclax will be summarized for the Safety and Efficacy Evaluable Populations. Point estimates and 2-sided 95% confidence intervals of CRMRD- rates will be reported.

## 9.10 Safety Review Committee

The SRC membership will be comprised of Investigators (and/or designated representatives), the Sponsor's Medical Monitor, safety physician, clinical scientist, and the study manager. Ad hoc attendees may include the study PK scientist, biostatistician, and translational research scientist. Other internal and external experts may be consulted by the SRC, as necessary.

The SRC will recommend dose escalation/de-escalation decisions in Part A. The decision to evaluate additional subjects within a dose cohort, smaller dose increments, alternate dosing schedules, or make a recommendation of the preliminary dose and schedule of CC-95251 to test in the expansion cohorts (Parts B and C) will also be at the discretion of the SRC, based on their review of available safety, tolerability, PK, PD, and preliminary efficacy. During dose expansion phase, the SRC will continue to review safety data regularly throughout the study and make recommendations about study continuation, dose modification and establishment of a RP2D as appropriate.

All decisions made by the SRC at the dose escalation meetings will be formally documented (via meeting minutes and memos) and circulated to all sites in writing. No dose escalation, de-

escalation, change of dosing schedule, or expansion of existing dose cohorts will commence prior to written notification having been sent to participating sites of the respective SRC decision(s).

The meeting frequency will depend on enrollment rate and when dosing decision milestones are reached in the dose escalation part and when a meaningful amount, as decided by the SRC, of safety/efficacy data are available after dose escalation.

The Sponsor has implemented a comprehensive safety process that is appropriate in managing subject safety at this stage of development: a multi-layered process to ensure safety monitoring through close collaboration of study site investigators, the BMS study team, and the Worldwide Patient Safety-led SMT. To support safety oversight, the Sponsor has established processes for collection, ongoing review, analysis, and submission of individual AE reports and their aggregate analyses. Because this is an open-label study, the BMS safety physicians, Medical Monitors, and the investigators will have access to all data necessary for real-time safety evaluation.

